### 3.2 Exclusion Criteria

- Allergy to granisetron or other 5HT3RA drugs
- Previous allergic reactions to any drug skin patches
- Recent (less than 1 month) or current chemo- or radiotherapy
- Any nausea, vomiting, or retching within 24 hours prior to anesthesia
- Any type of eye surgeries
- History or diagnosis of gastrointestinal obstruction or ileus
- History of serotonin syndrome
- Unable to sign consent

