## 2.3 Study Rationale

Clinical guidelines recommend the use of 5HT3RAs in the prevention of PONV and chemotherapy-induced nausea and vomiting (CINV). Granisetron is a potent 5HT3RA, with little or no affinity for other serotonin receptors, or for dopamine-D2, histamine-H1, benzodiazepine and opioid receptors.

Oral and intravenous (iv) formulations of granisetron have been marketed for over 15 years. They are licensed for the prevention of PONV and nausea and vomiting associated with initial and repeat courses of emetogenic cancer therapy, including high-dose cisplatin, which has a strong emetic effect in more than 90% of patients.

ProStrakan, Limited has developed a new granisetron formulation, Sancuso® , a transdermal delivery system (TDS) (granisetron TDS or patch) for the prevention of CINV. Sancuso® consists of a stable matrix of granisetron base (6% w/w) in a commercially-available adhesive (DURO-TAK ® 387-2287), designed to sustain delivery of granisetron over a number of days following topical application. Pharmacokinetic evaluation of Sancuso ® has indicated that it provides continuous delivery of granisetron over 7 days, providing exposure similar to an oral dose of 2 mg per day (Howell et al, 2009). Previous data indicate prolonged activity of this preparation in prophylaxis of CINV. There is no data available about the efficacy of this formulation in the prophylaxis of PONV.

It should be noted however that there is increasing concern among anesthesiologists and surgeons about patients displaying so called post-discharge (or late) form of PONV. These symptoms occur at least 48-72 hours after the procedure and may last several days (often after patient has been already discharged from the medical facility). It is therefore feasible that the investigated formulation of granisetron will provide prophylactic antiemetic activity throughout the entire period, including acute and delayed phases of PONV.

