## 3.0 Inclusion and Exclusion Criteria

### 3.1 Inclusion Criteria

- Patients that are between the ages of 18 and 89
- Scheduled to undergo surgical procedures with general anesthesia
- Seen in the anesthesia clinic at least 24 hours before surgery
- History of severe PONV after previous general anesthesia
- Surgical procedures with anticipated duration > 1 hour and no more than 5 hours
- American Society of Anesthesiologists (ASA) physical status I to III

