### **4.4 Eligibility/screening of subjects**

A detailed PONV history will be used to determine occurrence/severity of previous PONV during patient's history and physical evaluation in the Clinic (as it is done anyway for all surgical patients seen in APEC). In general the eligible patients experienced 1 or more episode of PONV with general anesthesia requiring additional treatment in PACU or had episodes of PONV after discharge from PACU or discharge from hospital.

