#### **7.2.1 Visit 1 - Anesthesia Preoperative Evaluation Clinic and recruitment and drug dispensation**

Patient is seen in clinic and identified as having a history of serious PONV, in particular delayed or post discharge PONV. Study will be explained to the patient and consent obtained. The investigational pharmacy will be notified that a study patient has been enrolled and they will prepare the patches for distribution to the patient. EKG will be performed and the results will be recorded preoperatively.

A member of the research team will obtain the assigned patches from the investigational pharmacy and deliver to the anesthesia provider (member of the research team).

The provider will then demonstrate to the patient how to apply the patch and the patient can practice using a placebo patch to show that the correct placement. Patient will then take the actual patch home with them. Patient will also be given a PONV diary to take home with them. Upon returning home from surgery, the patient will be asked to record their instances of nausea and vomiting on a daily basis for up to five days after surgery. At hour 120 post-op, a case manager will telephone the patient and note any recorded

instances of nausea and vomiting since the patient has returned home. The case manager will also check the status of the patch and any medications that were taken as a result of nausea and vomiting. One week after removal of patch (120h post-op + 7 days), a case manager will call the patient a final time to collect adverse events and to assess patient satisfaction with the patch.

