###### **7.4.6.3 Preparation and Dispensing**

Upon enrollment, the PI will write a prescription for the patch and that will be faxed to the pharmacy. The pharmacy will assign a patch to the patient and a member of the research team will pick that up from the pharmacy and deliver it to the anesthesiologist (research team member). The provider will then educate the patient on how to apply the patch to the upper arm

area. The patient will have the opportunity to practice applying the patch using a placebo patch (supplied by the sponsor). The patient will then take the patch home and apply at minimum 24 – 48 hours before surgery as hours (no longer than 48 hours) before surgery.

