## **11.5 Individual's reviewing the data**

Oversight for the conduct of the study will be provided by the PI and the research coordinator will monitor the data. They will ensure that all eligible criteria and consent requirements are met prior to a subjects' participation in the study and that the procedures and adverse event reporting occur according to the IRB approved protocol.

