## **12.0 Risks**

### **12.1 CONTRAINDICATIONS**

Sancuso is contraindicated in patients with known hypersensitivity to granisetron or to any of the components of the patch.

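### The exclusion list in Section 3.2 does not carry over the whole of the contraindication in Section 12.1: known hypersensitivity to a patch component, learned other than through a drug patch, is not excluded in writing

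*Combined protocol and SAP*

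**What the plan says.** Section 12.1 states the contraindication in two parts: "Sancuso is contraindicated in patients with known hypersensitivity to granisetron or to any of the components of the patch".

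Section 3.2 has two exclusions that bear on this. One is allergy to granisetron or to other drugs of its class. The other is "Previous allergic reactions to any drug skin patches". Nothing else in Section 3.2, and nothing in the inclusion criteria of Section 3.1, concerns allergy to the materials of the patch.

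Section 2.3 shows that the patch has a component besides the drug. It describes granisetron base at 6% w/w in a "commercially-available adhesive (DURO-TAK ® 387-2287), designed to sustain delivery of granisetron".

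Before the active patch leaves the clinic, the protocol describes these steps:

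- a PONV history taken within the routine history and physical, "as it is done anyway for all surgical patients seen in APEC" (Section 4.4);
- a demonstration, after which "the patient can practice using a placebo patch to show that the correct placement" (Section 7.2.1);
- a prescription: "Upon enrollment, the PI will write a prescription for the patch and that will be faxed to the pharmacy" (Section 7.4.6.3).

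Section 11.5 has the investigator and the coordinator make sure that eligibility criteria are met before participation, and that "procedures and adverse event reporting occur according to the IRB approved protocol".

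**The concern.** A contraindication names people who must not receive the product. An exclusion list is what screening staff and monitors work from. When the list is narrower than the contraindication, a patient can be correctly recorded as eligible and still be someone the same protocol says should not wear the patch.

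The gap here lies in the second part of Section 12.1. The exclusion in Section 3.2 asks about a past event with one type of product. The contraindication asks about a known state, however it came to be known. Someone whose allergy to an adhesive component was found through a non-drug product or through testing falls between the two.

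What is at stake is an avoidable allergic reaction in a participant. The patch is applied at home, 24 to 48 hours before surgery (Section 7.2.2), so exposure begins away from the study team.

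**Working it through.** No calculation applies to the main point, and the plan gives no figure to reproduce. The check sets the two lists side by side and then looks for a step elsewhere that closes any difference.

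**1. The lists compared**

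| Contraindicated in Section 12.1 | Counterpart in Section 3.2 | Covered? |
|---|---|---|
| Known hypersensitivity to granisetron | Allergy to granisetron or another drug of the class | Yes, and more widely than needed |
| Known hypersensitivity to a patch component, shown by an allergic reaction to a drug patch | Past allergic reaction to any drug skin patch | Yes, and more widely, since any drug patch counts whatever caused the reaction |
| Known hypersensitivity to a patch component, learned in any other way | None | No |

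The third row is the gap. It is not empty by construction, because Section 2.3 names an adhesive as part of the patch.

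**2. Steps before exposure**

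- *History and physical (Section 4.4).* The section describes a history directed at PONV. A routine allergy history may bring the allergy to light, but the text does not ask for it.
- *Placebo-patch practice (Sections 7.2.1 and 7.4.6.3).* Its stated purpose is to teach placement. It is not described as a sensitivity test. The composition of the practice patch is not given; if it uses the same adhesive, the practice would itself be a contact.
- *Prescription (Section 7.4.6.3).* It is written upon enrolment, hence after eligibility has been decided. No allergy check is attached to it.
- *Eligibility oversight and monitoring (Sections 11.5 and 22.1.1).* Both confirm the written criteria. A patient in the third row meets those criteria, so a check confined to them would raise nothing.

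**3. Steps after exposure**

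Adverse event assessment starts once the patch is on (Section 11.4). The first scheduled look for side effects is on the day of surgery (Section 7.2.3). Patch removal for severe or generalised skin reactions (Section 12.2.2) and withdrawal for allergic reaction (Section 3.3.1) both respond to a reaction that has already happened.

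**4. The enrolment margin**

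Section 16.0 gives up to 80 enrolled and 60 evaluable, so the margin is 80 − 60 = 20, which that section describes as potential screen failures. Section 3.3.1 also provides for removal after enrolment: surgical complications, a patch not kept on, or allergic reaction. If removed patients do not count as evaluable, which Section 16.0 does not spell out, they come out of the same 20.

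**The case against.** The strongest reply is that Section 12.1 is itself current protocol text. The investigator prescribes for each patient individually, and Section 11.5 requires procedures to follow the approved protocol, which includes Section 12.1. On that view the restriction exists and only its place in the document is at issue. Much of this stands. A reader might infer from the comparison that the protocol allows contraindicated patients to be treated, or that such patients will be treated. The documents do not support either inference. What remains is that the list used for screening admits the patient, and the visible text leaves the catch to the prescriber without calling for the question.

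A second reply is that the drug-patch criterion is a sensible proxy. A patient can report a past patch reaction, whereas few could be expected to know their status for a particular adhesive grade. That is reasonable inference, and it is why the group is called narrow. It does not make the proxy complete, since the contraindication is about those who do know. It is also fair to add that reacting to some other adhesive product is not in itself hypersensitivity to a component of this patch.

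A third reply is that the product's skin record is reassuring: low sensitisation potential (Section 2.2) and generally mild site reactions (Section 12.2.2). This limits the concern, but the protocol does not say that those data include people already sensitised to a component.

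Finally, a reader might take the 24 to 48 hours between home application and the first scheduled check as a measure of the problem. It is not one. That interval applies to every participant and says nothing about how many are affected or how badly.

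**Conclusion.** The point holds as a minor, safety-only mismatch between Sections 3.2 and 12.1. Applied as written, the exclusion list admits a narrow group whom the same protocol calls contraindicated, and no visible screening step requires the check before home application.

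No magnitude is given. The documents report neither how common known component hypersensitivity is nor where else the adhesive is used. Sample size, primary endpoint and analysis are not touched.

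The conclusion rests on the visible text. Consent pages and data collection forms were not available, and a screening question could sit there. Confidence is high in the comparison of the two sections. Whether any patient would in practice go unnoticed cannot be judged from the documents.

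**What to change.** Keep both present exclusions and add one line to Section 3.2: *Known hypersensitivity to any component of the patch, including its adhesive.* Ask the matching question at Visit 1, before the placebo-patch practice and before the active patch is dispensed.

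The cost is one line of protocol text and one question at a visit that already takes place. There may be a few more screen failures, all of them before exposure. The 20 places between 80 and 60 should not be treated as spare room for these, because removals under Section 3.3.1 may draw on the same margin.

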### 3.3 Early Withdrawal of Subjects

#### 3.3.1 Criteria for removal from study

- Serious surgical complications during the patch administration preventing in obtaining follow-up results (including re-operation, admission to intensive care unit with intubation, death).
- Inability of patient of keep the transdermal patch for the entire study period (up to

- 120 hours postoperatively)
- Development of allergic reaction or hypersensitivity

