### **1.2 Primary Study Endpoints**

Number of complete responders (CR, defined as no nausea or vomiting/retching episodes during 120 hours postoperatively, no additional antiemetic medication up to 120 hours after surgery)

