#### **7.2.2 Visit 2 - approximately 24-48 hours preoperatively (patient's home)**

Patient will apply the patch to their upper arm 24-48 hours before scheduled surgical procedure, as instructed during their pre-op anesthesia visit. The patch will then remain in place until 120 hours after surgical procedure. No backup patch will be provided so the patients with the accidentally missing patch will need to call their primary surgical service for the standard antiemetic medication.

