### **9.0 Statistical Plan**

#### **9.1 Sample size determination**

We are planning an open label study of cases treated with granisetron patch (no comparison group, historical control group). Prior data indicate that the failure rate (at least 1 x PONV postoperatively or administration of additional antiemetics) among patients with severe PONV is 0.85. If the true failure rate for experimental subjects is 0.4 (decrease of incidence of PONV by half), we will need to study 60 experimental subjects to be able to reject the null hypothesis that the failure rates for experimental subjects is equal to historical control with probability (power) 0.8. The Type I error probability associated with this test of this null hypothesis is 0.05. We will use an uncorrected chi-squared statistic to evaluate this null hypothesis.

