#### **9.2 Statistical methods**

The Type I error probability associated with this test of this null hypothesis is 0.05. We will use an uncorrected chi-squared statistic to evaluate this null hypothesis.

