## 16.0 Number of Subjects

We require 60 evaluable patients, with an enrollment of up to 80 patients which would include a potential of 20 screen failures.

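### Treated patients can be removed for not keeping the patch, but the plan never says whether they stay in the complete-response denominator

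*Combined protocol and SAP*

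**What the plan says.** **Removal.** Section 3.3.1 lists three grounds for taking a patient out of the study, all of which can arise once the patch is on: a serious surgical complication that prevents follow-up results; "Inability of patient of keep the transdermal patch for the entire study period", which runs to 120 h after surgery; and an allergic or hypersensitivity reaction. Section 3.3.2 follows withdrawn patients for 7 days after patch removal. It does not say that nausea, vomiting and antiemetic use to 120 h are still collected, and Section 7.2 gives side effects as the purpose of the last call.

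**Numbers and analysis.** Section 16 states: "We require 60 evaluable patients, with an enrollment of up to 80 patients which would include a potential of 20 screen failures". *Evaluable* is defined neither there nor elsewhere. Section 9.1 sizes the trial on a "failure rate (at least 1 x PONV postoperatively or administration of additional antiemetics"). Section 9.2 gives the Type I error and the test ("We will use an uncorrected chi-squared statistic to evaluate this null hypothesis"), with no analysis set and no rule for missing outcomes.

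**Endpoint and data.** Section 1.2 requires no nausea, no vomiting or retching, and "no additional antiemetic medication up to 120 hours after surgery". Section 7.2.3 words CR differently: no emetic episode and no rescue, with nausea handled as a score change. Section 7.2.2 provides no spare patch, and "patients with the accidentally missing patch will need to call their primary surgical service for the standard antiemetic medication". Under Section 7.2.1, once home, "the patient will be asked to record their instances of nausea and vomiting on a daily basis for up to five days after surgery", and of the 120-h call it says: "The case manager will also check the status of the patch and any medications that were taken as a result of nausea and vomiting".

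**The concern.** Two readings are open. Under one, an evaluable patient is anyone who was not a screen failure, and removed patients count by their outcome. Under the other, a patient removed under Section 3.3.1 is not evaluable and leaves the CR calculation.

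The second reading would drop patients on something that happens after treatment starts and is linked to the outcome. A patient who loses the patch after surgery is directed to an antiemetic, which makes that patient a CR failure under Section 1.2; removal would then take the failure out of the denominator.

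The trial has one arm and a fixed historical rate, so no concurrent group shares the selection, and whatever denominator is chosen feeds straight into the CR estimate. That estimate is the main product of an open-label pilot. Keeping the patch on is also part of Aim 3 in Section 1.1, so CR among keepers alone would not describe the strategy being piloted.

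**Working it through.** **Inputs from the documents.** Historical failure rate 0.85, so CR 0.15; planned failure rate 0.40, so CR 0.60 (Section 9.1). Sixty evaluable patients, enrolment up to 80, 20 potential screen failures (Section 16).

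**Inputs assumed.** The documents give no removal rate, so m = 6 and m = 10 removed patients are illustrations, as is their failure rate f.

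**Step 1: the plan's own figures.** 80 − 20 = 60, so Section 16 assigns the whole margin to screen failures. The 60 in Section 9.1 does not follow from its stated inputs: at 80% power and two-sided 0.05, a one-sample normal approximation gives 7, and a two-sample comparison gives 17 per arm. That is a separate matter and does not bear on the denominator.

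**Step 2: CR if removed patients are dropped.** At the planned effect, 36 of 60 keepers respond: 60.0%, Wilson 95% CI 47.4% to 71.4%, half-width 12.0 points.

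**Step 3: CR over all treated patients.** CR = (36 + m(1 − f)) / (60 + m).

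| Removed | f = 0 | f = 0.4 (as keepers) | f = 0.7 | f = 1 |
|---|---|---|---|---|
| m = 6 | 42/66 = 63.6% | 39.6/66 = 60.0% | 37.8/66 = 57.3% | 36/66 = 54.5% |
| m = 10 | 46/70 = 65.7% | 42/70 = 60.0% | 39/70 = 55.7% | 36/70 = 51.4% |

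Dropping removed patients overstates CR by at most 60.0 − 54.5 = 5.5 points with 6 removed and 60.0 − 51.4 = 8.6 points with 10. It understates CR if removed patients do better than keepers, by at most 3.6 and 5.7 points.

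**Step 4: which direction the documents support.** For patch loss after surgery, Sections 7.2.2 and 1.2 together make f > 0.4 likely. It is not certain: a patient who loses the patch late, has no symptoms and takes nothing is still a responder. For loss before surgery, allergic reactions and complications, nothing in the documents fixes the sign.

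**Step 5: the test at the planned effect.** z = (CR − 0.15) / √(0.15 × 0.85 / n). For 36/66, 0.3955/0.0440 = 9.0; for 36/70, 0.3643/0.0427 = 8.5. Rejection stands even if every removed patient failed.

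**The case against.** The strongest reply is that the harmless reading is at least as well supported. Section 16 explains the gap between 80 and 60 by screen failures alone. If removals also had to come out of the 80, 6 removals would leave room for only 80 − 60 − 6 = 14 screen failures. The failure definitions in Sections 1.2 and 9.1 do not mention keeping the patch, and Section 3.3.1 nowhere says that outcomes already observed are discarded. All of this stands. A reader might infer that the plan is to analyze keepers only; the documents do not say so. The defect is that they do not rule it out, while a rule headed as removal from the study invites it.

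Second, the direction is argued for one subset only, and Section 7.2.2 does not say that every patient with a missing patch actually takes an antiemetic. This also stands. The table treats removals as one group with one failure rate, so its outer columns are bounds, not forecasts. A reader might infer that every removal inflates CR; the documents do not support that.

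Third, a shift of 2.7 points (6 removed, 70% failing) or 4.3 points (10 removed, 70% failing) is small beside a half-width of 12.0 in a pilot. That is fair as to size. But a selection error does not shrink with more patients and is not reflected in the interval, and closing the gap costs little.

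**Conclusion.** The concern holds in a limited form. The CR denominator is not stated, and following Section 3.3.1 literally could take likely failures out of a single-arm estimate. If removed patients are dropped, CR is probably overstated for patch loss after surgery; for the other removals the sign is unknown. The size cannot be derived from the documents. Under the assumed 6 or 10 removals, the bounds on all-treated CR against a reported 60% are those in the table, and they include zero error and the opposite sign.

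A reader might infer that the significance test is also compromised. At the planned effect it is not. It could be if the patch did not work: suppose true CR over all treated is 15%, every removed patient fails, and 60 keepers are analyzed. CR among keepers is then 0.15/(1 − q) for removed share q, and the exact chance of 15 or more responders in 60 (the cutoff for a two-sided 0.05 test) rises from 2.9% with no removals to 6.5% at q = 10% and 14.2% at q = 20%. This is a worst case on assumed shares; no removal rate and no such failure pattern stands in the documents, so it is not a finding about this trial.

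The gap should be fixed before the data are analyzed. Confidence is medium: the omission is plain from the text, but its effect depends on how many patients are removed and how they fare.

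**What to change.** 1. **Reconcile the endpoint first.** Sections 1.2 and 7.2.3 define CR differently (with and without nausea). Settle on one definition and use it throughout.
2. **Section 9.2.** State that the primary set is all patients who applied the patch and had general anesthesia; that each is classified by the observed 0–120 h outcome under the reconciled definition, whether or not the patch was kept; and that a missing outcome counts as non-response, with the number reported. Give patients who kept the patch to 120 h as a sensitivity analysis.
3. **Section 16.** Define *evaluable* as this primary set, and count removals under Section 3.3.1 separately from screen failures.
4. **Sections 3.3.1 and 3.3.2.** State that collection of nausea, vomiting and antiemetic use to 120 h (diary, and bedside or phone evaluation at 120 h) continues after patch loss or withdrawal.
5. **Section 7.2.1.** The diary and call wording covers only the time after returning home; extend it to the hospital stay. The call asks about medication taken because of nausea and vomiting, so also have it record an antiemetic taken only because the patch was missing.

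No rule on patch removal or patient care changes.

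**Cost.** Wording in these sections and a few extra outcome questions, mainly for withdrawn patients and hospital stays; Section 11.1 already reviews early terminations. The reported CR may be lower. Counting missing outcomes as non-response is slightly conservative: with 6 removed, one of them missing and the rest failing at 40%, CR is (36 + 5 × 0.6)/66 = 59.1% instead of 60.0%.
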